7.2 Baseline Testing/Prestudy Evaluation

7.2.1 Screening Visit (within 30 days of Day 1)

Newly diagnosed early stage breast cancer patients will be screened as potential participants from the University of Alabama at Birmingham, University of Wisconsin, University of Minnesota, University of Iowa, and Northwestern University. A history and physical examination will be performed as part of standard of care by providers at each institution.

The procedures to be performed to evaluate eligibility are:

- Invasive breast cancer or DCIS confirmed on pathology report; eligible participants must have invasive breast cancer between 0.5 cm and 5.0 cm in size based on imaging or for DCIS-only lesions, the imaging abnormality corresponding to the cancer must be at least 1.0 cm in size (i.e. calcifications, distortion or mass on mammogram, or mass or nonmass enhancement on MRI).
- Estrogen receptor status must be confirmed on pathology report. Estrogen receptor positivity defined as per 2010 ASCO-CAP Guidelines³⁶ – with at least 1% positive tumor nuclei in the sample on testing in the presence of expected reactivity of internal (normal epithelial elements) and external controls.
 - Eligible participants must have invasive breast cancer that is ER+ or ER-,
OR
 - Eligible participants must have DCIS that is ER+ and grade 3, or that is ER- and any grade.

*Beginning in November 2021, participants will be limited to estrogen receptor negative status.

- Her2neu status must be confirmed on pathology report for those with invasive cancer.³⁷ Her2neu status is defined as positive and negative based on the 2013 ASCO-CAP guideline. As recommended by the guideline, Her2neu equivocal results must have a reflex or new test to determine Her2neu status.
- Review of the participant's medical history.
- Measurement of height and weight.
- Evaluation of vital signs including temperature, pulse, blood pressure, and respiration rate.
 - For grade 1, grade 2, and non-persistent grade 3 hypertension, repeat blood pressure reading after 5 minutes.
 - If the average reading of the two measurements is grade 3 (systolic BP ≥ 160 mm Hg or diastolic BP ≥ 100 mm Hg) the patient is not eligible.
 - If the average reading of the two measurements is less than or equal to grade 2, then the participant is eligible.
 - If the average of the 2 readings is grade 1 or grade 2 hypertension, document the appropriate level hypertension on the baseline symptom form.
- A physical examination. A gynecologic examination may be waived. The physical examination may be performed by any healthcare professional (i.e. physician, nurse practitioner, physician assistant) who is allowed by local policy to perform physical examinations.
- Assessment of Performance Status, using the ECOG method (convert a Karnofsky score into an ECOG score using the scale in Appendix A).
- Review of concomitant medications including over the counter medications and nutrition supplements
- Review and discussion of study including review of informed consent document.

- Patients agreeing to participate in the study will sign the informed consent document.

After obtaining written informed consent, a participant is registered with CLO and assigned a unique PID number (see section 6.8) and eligibility evaluations may occur. Eligibility evaluations determine if the participant is a fit candidate for study participation. All eligibility evaluations (including labs) must be completed within 30 days of Day 1. The eligibility checklist is provided to each site to help determine if the participant is eligible for the trial.

- Administer the baseline version of tobacco and alcohol assessment questionnaire – Appendix D
- Perform the laboratory tests as outlined in section 7.1. Results from laboratory tests or physical examinations performed outside the context of the research study may be used to confirm eligibility, provided these procedures were conducted within 30 days of Day 1.
- A fasting or non-fasting lipid panel may be obtained, if drawn within 30 days of Day 1. If non-fasting lipid levels are outside of the range for eligibility, a fasting lipid panel can be drawn. For the fasting lipid panel, participants should be fasting for at least 10 hours prior to this draw.
- Collect urine and blood sample for baseline PK studies.
- Collect 30 mL blood sample for immune studies for participants 6-25.

If deemed eligible, follow the below mentioned procedures:

For the first 5 participants:

- a. Since the participants will be fasting for the laboratory tests, they can have a meal after blood draw for laboratory tests while they wait to get their laboratory results.
- b. Once the lab results are obtained to determine eligibility, dispense the study agent in 3 bottles of 30 capsules of 80mg each and administer the first dose of 240mg (3 capsules) at the clinic visit after minimum of 2 hours post their last meal. The participant will be able to eat again after both PK blood draws are performed. This will be considered as Day 1.
- c. Document the date and time in the pill diary and provide the diary to participant with instructions on how to complete.
- d. First post-dose PK sample of 3mL blood will be collected within 5 minutes of drug administration.
- e. Second post-dose PK sample of 3 mL blood will be collected 2 hours from the time the drug was taken. Participants should not eat between the PK blood draws.
- f. The study dose has to be taken in the evening on empty stomach (2 hours after last eating and wait for 1 hour before eating again), every day until the day before surgery.
- g. They will be provided with a BP monitor to measure BP at home. While they are in clinic, they will be instructed on how to use the monitor. The instructions are noted on the BP diary for reference at home (Appendix C). Participants will be asked to measure and document the blood pressure values in the BP diary on Day 7, Day 8 (approximately 24 hours later) and day prior to surgery. All BP measurements should be taken in the morning. They will be instructed to notify the study team if the value of the reading is Systolic \geq 160 or Diastolic \geq 100 (grade 3). The study coordinator will contact the participants on Day 8 by telephone to assess adverse events and other symptoms, review medications and review the BP readings.

For participants 6 onwards:

- a. Review guidelines for agent administration with the participant and provide the diary to participant with instructions on how to complete.
- b. Dispense study agent – 9CUAB30 based on the dose of the study determined by interim analysis. Participant will be given enough study drug for the duration of participation in the treatment phase of the study.
 - Dose 240mg (3 capsules) – dispense 3 bottles of 30 capsules each or

- Dose 160mg (2 capsules) – dispense 2 bottles of 30 capsules each.
- c. Participants may start taking the medication in the evening on the date of dispense, in the evening on empty stomach (2 hours after last eating and wait for 1 hour before eating again) until the day before surgery.
- d. They will be provided with a BP monitor to measure BP at home. While they are in clinic, they will be instructed on how to use the monitor. The instructions are noted on the BP diary for reference at home (Appendix C). Participants will be asked to measure and document the blood pressure values in the BP diary on Day 7, Day 8 (approximately 24 hours later) and day prior to surgery. All BP measurements should be taken in the morning. They will be instructed to notify the study team if the value of the reading is Systolic \geq 160 or Diastolic \geq 100 (grade 3). The study coordinator will contact the participants on Day 8 by telephone to assess adverse events and other symptoms, review medications and review the BP readings.

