3. SUMMARY OF STUDY PLAN

Eligible participants will be \geq 18 years of age and newly diagnosed pre- or post-menopausal patients with core biopsy proven invasive breast cancer between 0.5 cm and 5 cm in size or DCIS that is \geq 1.0 cm in size and is either Grade 3 ER+ DCIS or ER- DCIS of any grade

Patients agreeing to participate will take 9cUAB30 240 mg (160 mg contingent on interim analysis) by mouth daily for 14 – 28 days until the time of surgery. Tissue from the core biopsy will be used for the pre-treatment biomarker analysis. The tissue obtained from the surgical excision will be used for post-treatment biomarker analysis. We plan to enroll ER+ participants and ER- participants for a total of up to 41 participants undergoing intervention. We expect the study to be complete within 18-24 months. Beginning in November 2021, participants will be limited only to estrogen receptor negative status.

At baseline all participants will have a complete medical history, physical examination and review of concomitant medications. Participants will undergo laboratory testing to determine eligibility within 30 days prior to day 1 of the study. Baseline laboratory tests will include WBC, differential, hemoglobin,

hematocrit, platelets, INR, PTT, AST, ALT, total bilirubin, alkaline phosphatase, BUN, creatinine, calcium, glucose, albumin, electrolytes (Na, K, Co₂, Cl), HDL, LDL, total cholesterol, triglycerides, thyroid stimulating hormone, FT₃, and FT₄ (may omit any if collected as part of initial cancer workup documented in the medical record within 30 days of study Day 1). A plasma and urine sample for pharmacokinetic (PK) analysis will also be obtained. An additional 30 ml blood sample will be obtained to evaluate and measure the immune response of 9cUAB30 in participants 6-25.

For the first 5 participants, two extra plasma PK samples will be collected after administering the first dose of the study agent at 5 minutes and 2 hours post the drug administration to evaluate the C_{max}. After the first 5 participants complete study participation, their PK samples will be evaluated to determine the C_{max} and adverse events will be evaluated to determine safety of the 240mg dose. Based on this evaluation, it will be determined to continue study dose at 240mg or to reduce to 160mg (refer to section 13.9).

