7. CLINICAL EVALUATIONS AND PROCEDURES

7.1 Schedule of Events

Evaluation/ Procedure	Screening Visit	Day 1	Day 7	Day 8 (± 1 Day)	Day before surgery (-2 Days)	Surgery Day 15-29	7 days after surgery (± 1 Day)	4-5 weeks after surgery
Informed consent	X							
Assess eligibility	X							
Medical history	X							
Physical exam	X					X		
Vital signs/ height and weight	X ¹		X ²	X ²	X ²	X ¹⁰		
Laboratory tests ³								
- CBC with differential								
- PTT, INR								
- CMP						X ⁴		
- TSH/FT3/FT4								
- HDL/LDL/Chol/TG								
- FSH ⁵								
Urine for PK	X					X		
Plasma for PK	X	X ⁶				X		
Immunogenicity sample	X ⁷					X ⁷		
Concomitant medications	X			X	X	X	X	X
Dispense study agent	X							
Study medication start		X						
Collect study agent						X		
Providing drug diary and instructions	X							
Provide Blood Pressure monitors	X							
Review agent diary/record						X		
Adverse events	X			X	X	X	X	X
Telephone contact				X	X		X	X
Tobacco and Alcohol assessments	X ⁸					X ⁹		

1. Participant will be given a BP monitor, instructed on its use, and given instructions on recording and reporting BP readings. See section 11.1.1 Reportable AEs, for how the blood pressure should be obtained.
2. Home BP check (morning) only. For Day 7 and Day 8, the readings should be approximately 24 hours apart. If the participant has missed taking their BP reading on Day 7 and Day 8 they should be encouraged to note two readings on the following days at least 24 hours apart from each other.
3. CBC with differential will include WBC, differential, platelets, hemoglobin and hematocrit. CMP will include electrolytes (Na, K, Cl, CO₂) glucose, BUN, creatinine, calcium, albumin, total bilirubin, AST, ALT, alkaline phosphatase.
4. Participant must be fasting for 10 hours for the surgery Day 15-29 lab collection.
5. FSH will be collected for confirmation of post-menopausal status at screening for women under 60 who are amenorrheic for 12 or more months.
6. For first 5 participants only, plasma PK samples will be collected 5 minutes and 2 hours after the first dose has been administered.
7. For participants 6-25.
8. Appendix D – administer the baseline version of tobacco and alcohol assessments

9. Appendix D – administer the follow-up version of tobacco and alcohol assessments
10. Blood pressure on Surgery Day 15-29 will only be obtained if the Day before Surgery average blood pressure is above Systolic ≥ 120 or Diastolic ≥ 80 .

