7.4 Evaluation at Completion of Study Intervention

7.4.1 Day 15-29 (Pre-surgery – assessments must occur before surgery)

- Pre-surgery assessments may be completed up to 1 day prior to scheduled surgery (if surgery is scheduled for Monday, then pre-surgery assessments may be completed on Friday of the prior week). If pre-surgery assessments are completed prior to the day of surgery, the participant should be reminded that their last dose of medication should be the day before surgery.
 - If visit occurs on the day prior to surgery, pill bottles and diaries should be collected on the Day of Surgery to allow participant to take the last dose and document it.
- Evaluation of vital signs including temperature, pulse, and respiration rate.
 - Blood pressure on Surgery Day 15-29 will only be obtained if the average Day before Surgery blood pressure is above Systolic ≥ 120 or Diastolic ≥ 80 . An assessment of blood pressure should be collected using the study-supplied wrist monitor.
 - For grade 1, grade 2, grade 3 hypertension blood pressure readings, repeat blood pressure after 5 minutes. The average reading of the two measurements will be noted in the database and used for adverse event determination.
- A physical examination. A gynecologic examination may be waived. The physical examination may be performed by any healthcare professional (i.e. physician, nurse practitioner, physician assistant) who is allowed by local policy to perform physical examinations.
- Assessment of Performance Status, using the ECOG method (convert a Karnofsky score into an ECOG score using the scale in Appendix A).
- Administer the follow-up version of tobacco and alcohol assessment questionnaire – Appendix D
- Review of concomitant medications including over the counter medications and nutrition supplements.

- Perform the laboratory tests as outlined in section 7.1. The lipid panel (cholesterol, HDL cholesterol, LDL cholesterol, triglycerides) must be drawn after the participant has fasted for 10 hours (water is OK).
- Collect 10 mL urine and 3 mL blood for pharmacokinetic studies (prior to study medication dosing if the visit is 1 day prior to surgery)
- Collect 30 ml blood sample for immune studies for participants 6-25.
- Safety assessment and review of adverse events
- Pill accountability by the coordinator

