7.6 Methods for Clinical Procedures

- Participants will be fasting for 10 hours prior to serum lipid evaluation for the Day 15-29 Visit.

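### For participants 6 onwards the baseline lipid panel may be non-fasting while the only scheduled on-treatment panel must be fasting, so a within-person triglyceride rise can be understated

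*Combined protocol and SAP*

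**What the plan says.** **Baseline.** Section 7.2.1 states: "A fasting or non-fasting lipid panel may be obtained, if drawn within 30 days of Day 1". It continues: "If non-fasting lipid levels are outside of the range for eligibility, a fasting lipid panel can be drawn". Where a fasting panel is drawn, the fast is to be at least 10 hours. Section 3 adds that baseline tests, lipids included, need not be drawn for the study: "may omit any if collected as part of initial cancer workup documented in the medical record within 30 days of study Day 1". It sets no fasting condition for those results.

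**First 5 participants.** Later in section 7.2.1, the steps for this group begin: "Since the participants will be fasting for the laboratory tests, they can have a meal after blood draw". The steps for participants 6 onwards contain no such statement.

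**On treatment.** Footnote 4 of the schedule in section 7.1 reads: "Participant must be fasting for 10 hours for the surgery Day 15-29 lab collection". Section 7.4.1 repeats the 10-hour fast for the lipid panel, and section 7.6 says: "Participants will be fasting for 10 hours prior to serum lipid evaluation for the Day 15-29 Visit". Section 7.6 has no matching line for screening.

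**Use of the results.** Objective 1.2.7 compares safety with known retinoid toxicity, and section 8.3 lists hyperlipidemia among those toxicities. Section 13.5 makes the comparison qualitative and descriptive. Section 13.7 tabulates toxicity by severity. Section 13.9 reduces the dose if at least 2 of the first 5 have grade 2 hypertriglyceridemia, whatever the attribution.

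**The concern.** Sections 7.1 to 7.5 schedule one lipid panel before treatment and one after it starts; the Day 8 and post-surgery contacts are by telephone. For participants 6 onwards the two panels may be taken under different conditions. A non-fasting value within the eligibility range stays as the baseline, because the fasting redraw is optional and arises only when that value fails eligibility.

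The trial is single-arm, and the historical controls supply archived tissue, not blood. A participant's own baseline is therefore the only within-trial reference for her lipids. Section 2.2 describes hyperlipidemia as dose-limiting for the approved rexinoid, so this is a result that readers of objective 1.2.7 will look for. Section 2.2.4 already summarises the earlier volunteer study by reference to elevation from baseline.

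Baseline also matters for what becomes an adverse event. Under section 11.1.1.1, events are recorded once baseline assessments are complete. Under section 11, a laboratory value is reported only if a physician judges it clinically significant. A raised baseline makes a similar later value easier to regard as pre-existing.

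**Working it through.** The plan states no figure for lipid change, so there is nothing to reproduce. The check has three parts.

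**1. Fasting conditions side by side**

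| Group | Baseline panel | Day 15-29 panel |
|---|---|---|
| First 5 | Described as fasting, though the general bullet in 7.2.1 does not exempt them | 10-hour fast |
| Participants 6 onwards | Fasting, non-fasting or from work-up labs | 10-hour fast |

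Participants 6 onwards number 36 - 5 = 31 if the study stays at 240 mg, or 41 - 5 = 36 if it moves to 160 mg. These are upper limits on how many could have a non-fasting baseline; the documents do not say how many do. If the dose is reduced for toxicity, section 13.9 adds a further cohort of 5 evaluated only for toxicity. They would enrol after the first 5, under steps that require no fast at baseline.

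**2. Effect on a within-person change**

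Let d be the true proportional change on drug and f the proportional excess of a non-fasting value over the same person's fasting value. Both are assumptions. With a non-fasting baseline and a fasting follow-up:

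apparent change = (1 + d)/(1 + f) - 1

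Take d = 20%. As an example, a fasting baseline of 150 mg/dL rises to 180.

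- f = 10%: 180/165 - 1 = +9.1%
- f = 20%: 180/180 - 1 = 0.0%
- f = 30%: 180/195 - 1 = -7.7%
- f = 0 (fasting baseline): 180/150 - 1 = +20%

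If half the baselines are non-fasting, the geometric mean change is 1.2/(1 + f)^0.5 - 1, which gives +14.4%, +9.5% and +5.2%.

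Section 4.1 caps eligible triglycerides at 1.5 x ULN, and the redraw applies above that. I simulated this with every first draw non-fasting and every failing value redrawn fasting. The further assumptions were a ULN of 150 mg/dL, so a limit of 225, and fasting values lognormal with median 110 and log-SD 0.45, restricted to 225 or below. Non-fasting draws carried extra log-SD of 0.15.

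| f | Redrawn | Apparent change (true +20%) |
|---|---|---|
| 10% | 4.7% | +10.4% |
| 20% | 8.0% | +2.5% |
| 30% | 12.0% | -3.6% |

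Under these assumptions the redraw provision removes only a small part of the distortion.

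**3. The interim rule**

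For a true grade 2 rate p, the chance of meeting the triglyceride criterion is 1 - (1 - p)^5 - 5p(1 - p)^4. This is 0.081, 0.263 and 0.472 for p = 10%, 20% and 30%. The rule has no baseline term, so baseline fasting state does not enter.

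**The case against.** The strongest reply is that the plan contains no change-from-baseline lipid analysis. Toxicity is tabulated by severity, the retinoid comparison is qualitative, and the interim rule counts grades irrespective of attribution in a cohort described as fasting. The percentages above therefore distort no prespecified output. This stands, and it limits the weight of the point. It does not remove it: a descriptive safety comparison in a single-arm trial will still refer to baseline, and the decision to record a mild elevation as an event may do so too.

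Four stronger readings are tempting and are not supported.

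- A reader might infer that the design hides the class's key toxicity. The Day 15-29 value is fasting and standardised, so a raised value appears whatever the baseline was. The retained baseline is also capped at 1.5 x ULN.
- A reader might infer that the error must run towards finding no effect. The documents give no fasting/non-fasting difference. Offering a fasting redraw after a failing non-fasting value fits that direction but does not establish it.
- A reader might extend the point to glucose. Sections 2.2 and 8.3 do not name glucose among the toxicities of interest, so the documents give no consequence to attach to it.
- A reader might infer that exactly two panels exist per participant. A screening redraw is allowed, and section 7.3.3 allows a site evaluation for adverse events. One on-treatment panel is scheduled; others are possible.

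Feasibility is also a fair defence. Section 7.3.1 wants drug started as soon as eligibility is confirmed, to avoid delaying surgery, and accepting existing labs serves that aim. This argues for keeping non-fasting results for eligibility. It does not argue for using them as the safety reference when blood is already drawn before dosing for PK.

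**Conclusion.** The point holds in limited form. For participants 6 onwards, including any further toxicity cohort under section 13.9, the baseline lipid panel may be non-fasting and the scheduled on-treatment panel may not. A within-person triglyceride rise can then be understated, and a mild on-treatment elevation can be taken as pre-existing. A true +20% would read as +9%, 0% or -8% with every baseline non-fasting and 10%, 20% or 30% inflation. The size rests on those assumed values, on the assumed drug effect and on the unknown share of non-fasting baselines; the direction rests on non-fasting triglycerides being higher.

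The interim dose rule, the primary endpoint, the sample size and the grading of the fasting Day 15-29 value are not affected. This is a worthwhile, low-cost improvement to the evidence for objective 1.2.7.

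**What to change.** - **Sections 7.2.1 and 7.6:** state that a non-fasting lipid panel serves eligibility only. For participants still to be enrolled, draw the safety-baseline panel after the same 10-hour fast as at Day 15-29, before the first dose, at the already scheduled blood draw where possible.
- **CRF:** record fasting status for every lipid panel, if it is not already captured; the forms are not in the documents.
- **Sections 13.5 and 13.7:** for those already enrolled, base any description of lipid change or shift on participants with two fasting panels, and show the others separately.
- **Section 7.2.1:** reconcile the general bullet allowing a non-fasting panel with the statement that the first 5 are fasting.

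The cost is a fasting instruction, one data field and an occasional repeat lipid tube, with slightly fewer participants in the change summary. At Version 20, with enrolment limited to ER-negative participants since November 2021, the prospective part reaches only those not yet enrolled. The recording and reporting parts matter most for the rest.
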